2.3 Correlative Studies

1. To identify potential mutations and changes gene copy number associated with enzalutamide resistance in patients with high risk prostate cancer.
2. To identify gene expression patterns, splice variants, and gene signatures associated with enzalutamide treatment and enzalutamide resistance in patients with high risk prostate cancer.
3. To identify changes in the immune response with enzalutamide treatment.

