Normalization and summarization of data will be performed using the SCAN Algorithm. Genes with at least a 2-fold difference in expression will be selected. All statistical analysis will be performed using the MultiExperiment Viewer. Principal component analysis will be performed by eigenvalue decomposition of the 3 principal components for tridimensional classification of the samples and an unsupervised hierarchical cluster by Pearson's correlation will be selected to group the samples. The significance analysis of microarrays statistical technique will be performed for descriptive and comparative purposes. We will use the R package DESeq to perform differential gene expression analysis between response and nonresponse patients. We will use the R package GoSeq to perform over- and under-representation analysis (ORA) of gene sets taking length bias into account.

- Immune response signatures will be evaluated with the Affymetrix Gene Chip Array as described above. In addition, to examine the effect on T cell subsets, T cell turnover and T cell diversity, peripheral blood will be collected at pre-enzalutamide treatment, 5-weeks post-initiation of enzalutamide therapy at the time of fiducial marker placement, after 5 weeks of external radiotherapy, and at 4 months after completion of radiation therapy. T cell diversity will be performed using deep T Cell Receptor (TCR) sequencing and T cell turnover will be assessed by evaluating the number of TCR excision circles.

3 Study Design

*Leuprolide and enzalutamide for 24 months total.

*MRI– Multiparametric PET/MRI with DWI, DCE, Spectroscopy

#Biopsy will be performed at time of fiducial marker placement and at time of brachytherapy boost

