obtained. The additional risks and discomfort of the limited biopsy during the fiducial marker placement are minimal and include bleeding as a needle is already being introduced under ultrasound guidance for fiducial marker placement as part of the standard of care. If available, the biopsy should be mapped under MRI-guidance.

- Refer to section 5.0 for details regarding androgen deprivation therapy.

6.1.3 8 weeks after initiation of Androgen Deprivation Therapy

- Refer to section 4.0 for details regarding radiation therapy.
- Patients should complete the EPIC-26, PROMIS, and EQ-5D questionnaires up to 5 days before the first day of radiation therapy.
- AE assessment - all patients will undergo weekly assessment by the radiation oncologist for any signs of acute toxicity
- After 5 weeks of conventional whole pelvic radiotherapy, patients should complete the EPIC-26, PROMIS, and EQ-5D questionnaires.
- After 5 weeks of conventional whole pelvic radiotherapy, brachytherapy may be performed as part of the radiation boost procedure (phase 2). At the time of brachytherapy, a biopsy of the dominant lesion(s) may be performed. The risks and discomfort of the limited biopsy are minimal as multiple catheters (larger in diameter) are already being introduced under ultrasound guidance into the prostate as part of the HDR procedure.
- After 5 weeks of conventional whole pelvic radiotherapy and within the first 3 days of phase 2 boost procedure (days 1-3), 50 ml blood collection will be performed.

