6.1.5 Discontinuation of Therapy

If a patient experiences a \geq Grade 3 toxicity or an intolerable side effect, withhold dosing for one week and until symptoms improve to \leq Grade 2, then resume at the same or a reduced dose (120 mg or 80 mg), if warranted.

In addition, the following safety/compliance events will result in the removal of patients from therapy either permanently or until the etiology of the problem has been identified and resolved:

- Any adverse event that is intolerable to the patient and that cannot be ameliorated by the use of adequate medical intervention, or that in the opinion of the investigator would lead to undue risk to the patient if dosing continued.
- Any seizure
- Creatinine >4.0 mg/dL
- Liver function tests (AST, ALT, or total bilirubin) >2 times the upper limit of normal
- An absolute neutrophil count $\leq 750/\mu\text{L}$
- A platelet count of $<50,000/\mu\text{L}$
- Patients who are in the opinion of the investigator or the medical monitor non-compliant with the protocol's requirements

The Investigator will withdraw a patient whenever continued participation is no longer in the patient's best interests. Reasons for withdrawing a patient include, but are not limited to, disease progression, the occurrence of an adverse event or a concurrent illness, a patient's request to end participation, a patient's non-compliance or simply significant uncertainty on the part of the Investigator that continued participation is prudent. There may also be administrative reasons to terminate participation, such as concern about a patient's compliance with the prescribed treatment regimen.

Table 6: Schedule of Assessments

| Study Assessments | Pre-Radiation Treatment | | During Radiation | Post-Radiation Treatment |
|--|-------------------------|--|---|--|
| | Baseline (Diagnosis) | 4-6 week after initiation of ADT (at placement of fiducial marker) | At Time of Brachytherapy Procedure (After fractionated whole pelvic radiotherapy) | Each follow up visit (6 wk, month 3-4, month 6, month 12, month 18, month 24, and month 36) ^a |
| Detailed medical history and physical exam | X | | | X (pertinent interval history and physical exam) |
| Collection of archival biopsy tissue if available | X | | | |
| TRUS biopsy of dominant lesion(s) ^b | X | X | X | |
| Serum PSA, testosterone | X | X | X | X |
| CBC with differential | X | X | X | X |
| Basic Metabolic Panel | X | X | X | X |

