8.1 Specimen Collection Summary for Translational Research

| Specimens Taken From Patient | Time of Collection |
|--|--|
| Diagnostic Core Biopsy Specimen(s) | 1) Pre-treatment 2) 4-6 wks after initiation of androgen deprivation therapy (at time of fiducial marker placement) 3) At the time of brachytherapy (if brachytherapy is being performed) |
| Whole blood: 50 mL of whole blood will be collected into green top tubes (sodium heparin). This should be collected, if possible, at the time of each blood draw for PSA and testosterone. | 1) Pre-Treatment 2) 4-6 wks after initiation of androgen deprivation therapy (at time of fiducial marker placement) 3) Within first 3 days of phase 2 brachytherapy 4) Month 3-4 post-radiation therapy |

Core biopsy specimens will be snap frozen in liquid nitrogen and stored at -80°C.

Plasma and whole blood samples will be processed and stored frozen at -80°C.

All samples will be de-identified and labeled with a case number. Samples will be sent frozen on dry ice via overnight carrier stored in a locked -80 °C freezer.

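### The third research blood draw is not fixed relative to the boost, and the T cell measures have no stated denominator or common sequencing depth

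*Combined protocol and SAP*

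**What the plan says.** Correlative objective 3 (section 2.3) reads "To identify changes in the immune response with enzalutamide treatment". Section 2.4.3 sets out the blood work for it: "to examine the effect on T cell subsets, T cell turnover and T cell diversity, peripheral blood will be collected at pre-enzalutamide treatment", then at 5 weeks of enzalutamide, then "after 5 weeks of external radiotherapy, and at 4 months after completion of radiation therapy". The assays take one sentence. On turnover it says "T cell turnover will be assessed by evaluating the number of TCR excision circles"; on the other measure its words are "T cell diversity will be performed using deep T Cell Receptor (TCR) sequencing". No unit, input amount, sequencing depth or diversity index is given there. Section 8 adds only a fixed blood volume of 50 mL per draw, and section 9.4 has no analysis for the immune endpoint.

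The third draw is timed differently elsewhere. Section 6.1.3 says that, after the five weeks of pelvic treatment and "within the first 3 days of phase 2 boost procedure (days 1-3), 50 ml blood collection will be performed". The specimen table in section 8.1 says "Within first 3 days of phase 2 brachytherapy", and Table 6 puts this draw in a column for the brachytherapy procedure.

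Table 2 (section 4.1.2) allows four boost modalities: IMRT, SBRT, permanent seed implant and HDR brachytherapy. The synopsis gives one day for a brachytherapy boost. Table 6 schedules "CBC with differential" in all four of its column groups, but nothing links that count to the T cell assays.

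**The concern.** There are two separate gaps.

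The first is timing and needs no biological assumption. Section 2.4.3 defines the third time point as the state after pelvic external-beam treatment. A window covering days 1-3 of a one-day boost also admits samples taken after the implant and its dose. Which state is sampled would then depend on logistics and boost modality, patient by patient.

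The second is measurement. A TREC count per volume of blood is the product of how many T cells there are and how many TRECs each carries. The number of distinct receptors observed depends on how many T cells are sequenced. If pelvic radiotherapy lowers circulating T cells (an assumption; the documents give no figures), either quantity can fall at draws 3 and 4 with no change in T cell biology. The study is single-arm and every patient also receives leuprolide and radiotherapy, so no control group would expose the artefact. At stake is the reading of correlative objective 3 at those two draws.

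**Working it through.** The plan states no figure for this endpoint, so there is none to reproduce. The timing texts can be set side by side, and the measurement point can only be illustrated.

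**Timing of draw 3**

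- Section 2.4.3: after five weeks of external treatment; boost not mentioned.
- Section 6.1.3: days 1-3 of the boost, any modality.
- Section 8.1: first three days of brachytherapy. Table 6: at the brachytherapy procedure. Neither gives a time for an IMRT or SBRT boost.

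Boost dose already received at a draw inside the section 6.1.3 window, using the Table 2 prescriptions:

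- HDR, 15 Gy in one fraction: 0 or 15 Gy.
- SBRT, 2 × 9.5 Gy: 0, 9.5 or, if both fractions fall inside three days (spacing not stated), 19 Gy.
- IMRT, 1.8 Gy fractions, assuming one per day: from 0 to 3 × 1.8 = 5.4 Gy.
- Seed implant: before the implant, or with the sources in place.

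One nominal time point therefore covers several exposure states.

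**Which draws radiotherapy can affect**

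Draw 1 is before treatment. Draw 2 is at 4-6 weeks, so by day 42, at fiducial marker placement (days 31-37 in the design schema). Radiotherapy starts on days 53-67. The general ±14-day visit window would stretch day 42 to day 56, but the markers are placed to position the patient for radiotherapy, which keeps draw 2 ahead of it. Only draws 3 and 4 follow pelvic treatment.

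**TREC number (illustration)**

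TRECs per mL = (TRECs per T cell) × (T cells per mL). Hold TRECs per T cell constant and assume T cells fall by f = 20%, 40% or 60%:

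- per mL, 1 − f: 0.80, 0.60, 0.40 of baseline;
- per T cell: 1.00 throughout.

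For a fixed amount of mononuclear-cell DNA, with T cell share s at baseline and the other cells falling by g, the ratio is (1 − f) / [s(1 − f) + (1 − s)(1 − g)].

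- Only T cells fall (g = 0), s = 0.5, f = 0.6: 0.4 / (0.2 + 0.5) = 0.57.
- Only T cells fall, s = 0.7, f = 0.2: 0.8 / (0.56 + 0.3) = 0.93.
- All cells fall equally (g = f): 1.00.

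The shares of 50-70% are assumed.

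**Receptor diversity (illustration)**

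An unchanged repertoire of 1,000,000 clones (Zipf, exponent 1) was sampled at 200,000 cells at baseline, then at 20%, 40% and 60% fewer:

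- observed richness: 0.83, 0.66, 0.48 of baseline;
- richness after down-sampling both samples to 50,000 cells: 1.01, 0.99, 0.99;
- Shannon entropy: 0.99, 0.98, 0.96.

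Richness is sensitive to cell number, entropy hardly at all, and down-sampling removes the artefact in richness.

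**The case against.** The strongest reply is that silence is not a bad method. A reader might infer that the plan uses an unadjusted TREC count. The text does not say so: counting TRECs is compatible with a per-cell or per-DNA result, and a laboratory may well sequence a fixed input. Nor need the blood count limit the input. At an assumed 0.2-1.5 million T cells per mL, 50 mL holds 10-75 million, and still 3 million at the low end after a 70% loss (10 × 0.3). This stands. The gap is an unstated rule, and the richness illustration applies only if sequenced cells fall in step with the blood count.

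A reader might also infer that objective 3 would probably show a spurious significant change. A paired t-test on 47 pairs, with an SD of log change of 0.5-0.8, does reach p < 0.05 in 85-99.8% of trials for a 30% T cell fall. But section 9.4 plans no such test, the 47 in section 9.2.1 belongs to the toxicity precision statement, and section 1.4 calls the immune work exploratory. The result also follows the inputs: a 10% fall gives 14-29%, and a 30% fall with 24 pairs and SD 0.8 gives 55%. The documents do not support a probability of this kind.

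On timing, section 6.1.3 can be read as making the section 2.4.3 time point operational, and it is tighter than the general ±14-day window. That is fair, but it does not settle whether the sample comes before or after the boost dose, and section 8.1 still omits two of the four modalities.

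**Conclusion.** The timing point holds on the text alone. As written, draw 3 may be taken before or after the boost, so its samples can mix two states, and section 8.1 sets no time for IMRT or SBRT patients. How many patients fall on each side, and what the boost does to the measures, cannot be worked out from the documents.

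The measurement point holds as an omission with a possible consequence. With no TREC denominator and no equal-depth rule, a fall in T cells after radiotherapy could be mistaken for a change in turnover or clone richness at draws 3 and 4. The illustrated sizes rest on an assumed 20-60% T cell fall, an assumed repertoire and, for TRECs, the unit chosen. Entropy-type indices are affected little.

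It would go too far to conclude that objective 3 as a whole is compromised. Draws 1 and 2 both precede radiotherapy, so the contrast closest to the objective escapes this effect, although it reflects enzalutamide plus leuprolide rather than enzalutamide alone. This is a minor correlative-endpoint issue. The primary PSA response analysis and the sample size of 53 are unaffected.

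**What to change.** - **Sections 6.1.3 and 8.1, with Table 6 to match:** take the third research sample after the last pelvic fraction and before the implant or first boost fraction, for every boost modality.
- **Section 2.4.3, TRECs:** report them per fixed T cell or DNA input rather than per blood volume, with the lymphocyte count from the scheduled CBC with differential alongside.
- **Section 2.4.3, diversity:** down-sample each patient's receptor samples to a common depth before comparing them.
- **Section 2.4.3, contrast:** treat baseline versus 4-6 weeks as the comparison for enzalutamide plus leuprolide before radiotherapy, and describe draws 3 and 4 as following the combined treatment.

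No extra draw is needed. The costs are a narrower window for draw 3 and some discarded sequencing depth. A DNA denominator removes the artefact fully only if other cells fall in proportion, as the 0.57-0.93 range shows. A true per-T-cell figure needs a T cell fraction, which the CBC does not give; the plan mentions T cell subsets but names no assay for them.

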3.1 Characteristics

This is a phase II study to evaluate the safety, toxicity, and feasibility of the addition of enzalutamide to leuprolide for a total duration of 24 months in patients with high-risk prostate cancer or pelvic node positive disease receiving radiotherapy. High-risk prostate cancer is defined as 2 or more of the following characteristics: 1) cT3a/b, 2) PSA ≥ 20 and < 150 , 3) Gleason 8-10, and 4) $\geq 33\%$ core involvement.

Pre-Radiation Treatment

To be eligible, patients must have biopsy proven prostate cancer. MRI/US fusion-guided biopsy is encouraged, but not mandatory, of the dominant lesion(s), if available. Patients must also undergo serum PSA and testosterone measurement < 45 days prior to biopsy or at least 18 days after biopsy. The serum PSA half life is 2.2 days, therefore any elevation due to biopsy or instrumentation of the prostate should resolve by 18 days (> 5 half-lives). Patients must undergo blood sample collection prior to initiation of androgen deprivation therapy. All patients should complete the EPIC-26, PROMIS, and EQ-5D questionnaires prior to enrollment. Enrollment will begin once standard staging including above studies are completed.

4-6 wks after initiation of ADT

Patients will undergo repeat PSA and testosterone testing at 4-6 weeks after initiation of ADT. Blood collection should be performed at the time of PSA and testosterone testing. Patients should undergo fiducial marker placement to optimize patient positioning and account for prostate motion for future radiation treatment. During the fiducial marker procedure, a biopsy of the dominant lesion(s) will be obtained. The risks and discomfort of the limited biopsy are minimal as a needle is already being introduced under ultrasound guidance for fiducial marker placement as part of the standard of care. The biopsy should be mapped under MRI-guidance if available.

At time of brachytherapy (if being performed)

After 5 weeks of conventional whole pelvic radiotherapy, brachytherapy may be performed. At the time of brachytherapy, a biopsy of the dominant lesion(s) will be performed. The risks and discomfort of the limited biopsy are minimal as multiple catheters (larger in diameter) are already being introduced under ultrasound guidance into the prostate as part of the HDR procedure. Patients should complete the QOL questionnaires including EPIC-26, PROMIS, and EQ-5D.

Post-Radiation Therapy

Serum PSA and testosterone should be measured at each follow up visit as described. These follow-up visits should occur at 6 wks post-treatment, 3-4 months, 6 months, 12 months, 18 months, 24 months, and at 36 months.

Number of Subjects

A total of 53 patients with high-risk prostate cancer or with pelvic nodal involvement without distant metastases will be enrolled.

3.2 Eligibility Criteria

Patients must have baseline evaluations performed prior to the first dose of study drug and must meet all inclusion and exclusion criteria. In addition, the patient must be thoroughly informed about all aspects of the study, including the study visit schedule and required evaluations and all regulatory requirements for informed consent. The written informed consent must be obtained from the patient prior to enrollment. The following criteria apply to all patients enrolled onto the study unless otherwise specified.

3.2.1 Inclusion Criteria

1. Histologically confirmed diagnosis of adenocarcinoma of the prostate within 25 weeks prior to registration at very high risk of recurrence as determined by 2 or more of the following combinations:
 - cT3a/b
 - PSA \geq 20
 - Gleason score 8-10
 - \geq 33% core involvement

OR

any patient with pelvic lymph node involvement \geq 1cm as determined by pelvic CT or MRI imaging will meet eligibility criteria for enrollment.

2. Standard staging exams for patients with high-risk prostate cancer including bone scan or NaF PET/CT scan, and pelvic and prostate MRI.
3. No distant metastases (M0) on bone scan or NaF PET/CT within 14 weeks prior to registration. Equivocal bone scan findings are allowed if the physician determines that distant metastases are unlikely based on clinical judgment.
4. Zubrod Performance Status 0-2 within 14 weeks prior to enrollment.
5. Age ≥ 18
6. CBC with differential obtained within 14 weeks prior to registration on study, with adequate bone marrow function defined as follows:
 - a. Absolute neutrophil count (ANC) $\geq 1,800$ cells/mm³
 - b. Platelets $\geq 100,000$ cells/mm³
 - c. Hemoglobin ≥ 8.0 g/dl (The use of transfusion or other intervention to achieve Hgb ≥ 8.0 g/dl is acceptable)
 - d. Serum creatinine < 2.0 mg/dl and creatinine clearance > 40 mL/min
 - e. Bilirubin $< 1.5 \times$ ULN
 - f. ALT or AST $< 2 \times$ ULN
7. Patients, even if surgically sterilized (i.e., status post vasectomy), who:
 - a. Agree to practice effective barrier contraception during the entire study treatment period and for 4 months (120 days) after the last dose of study drug, or
 - b. Agree to completely abstain from intercourse
8. Patient must be able to provide study-specific informed consent prior to study entry.

3.2.2 Conditions for Patient Ineligibility

- 1) Definite evidence of metastatic disease
- 2) Prior radical prostatectomy or bilateral orchiectomy for any reason
- 3) Prior invasive malignancy (except non-melanoma skin cancer) unless disease-free or not requiring systemic therapy for a minimum of 3 years.
- 4) Prior systemic chemotherapy for prostate cancer (Note that prior chemotherapy for a different cancer is allowed).
- 4) Prior radiotherapy, including brachytherapy, to the region of the prostate that would result in overlap of radiation therapy fields.
- 5) Previous hormonal therapy such as LHRH agonists (e.g. goserelin, leuprolide), anti-androgens (e.g. flutamide, bicalutamide), estrogens (e.g. DES), or surgical castration (orchiectomy)

- 6) Known hypersensitivity to enzalutamide or related compounds
- 7) History of adrenal insufficiency
- 8) Patients who are sexually active and not willing/able to use medically acceptable forms of contraception; this exclusion is necessary because the treatment involved in this study may be significantly teratogenic.
- 9) Prior allergic reaction to the drugs involved in this protocol.
- 11) Cushing's syndrome
- 12) Severe chronic renal disease (serum creatinine >2.0 mg/dl and confirmed by creatinine clearance <40 mL/minute)
- 13) Chronic liver disease (bilirubin >1.5x ULN, ALT or AST >2x ULN)
- 14) Active/Uncontrolled Viral Hepatitis
- 15) Chronic treatment with glucocorticoids within one year.
- 16) History of seizure including febrile seizure or any condition that may predispose to seizure (e.g., prior stroke, brain arteriovenous malformation, head trauma with loss of consciousness requiring hospitalization). Also, current or prior treatment with antiepileptic medications for the treatment of seizures or history of loss of consciousness or transient ischemic attack within 12 months prior to randomization.
- 17) Clinically significant cardiovascular disease including:
 - a. Myocardial infarction within 6 months prior to screening
 - b. Uncontrolled angina within 3 months prior to screening
 - c. Congestive heart failure NYHA class 3 or 4, or subjects with history of congestive heart failure NYHA class 3 or 4 in the past, unless a screening echocardiogram or MUGA scan performed within 3 months results in a left ventricular ejection fraction that is $\geq 45\%$;
 - d. History of clinically significant ventricular arrhythmias (e.g. ventricular tachycardia, ventricular fibrillation, torsades de pointes);
 - e. History of Mobitz II second degree or third degree heart block without a permanent pacemaker in place;
 - f. Uncontrolled hypertension as indicated by a resting systolic blood pressure >170 mm Hg or diastolic blood pressure >105 mm Hg at screening. Patients with initially elevated systolic blood pressure >170 mm Hg or diastolic blood pressure >105 mm Hg are eligible if they undergo medical management and are re-screened.

